## 46 INTRODUCTION

47 Stiffness after total knee arthroplasty (TKA) occurs when patients have difficulty flexing and  
48 extending their knee for routine activities of daily living. Patients require 67 degrees of knee  
49 flexion during the swing phase of gait, 83 degrees to ascend stairs, 90 degrees to descend stairs  
50 and 93 degrees to rise from a standard chair. When less than 90 degrees of motion is reached  
51 after TKA, the quality of life for patients is substantially decreased since simple activities like  
52 walking can become difficult.

53

54 Despite advancements in surgical technique, implant design and pain management, arthrofibrosis  
55 (i.e., malignant stiffness) remains one of the top five reasons for revision TKA. At the upcoming  
56 2016 American Academy of Orthopaedic Surgeons annual meeting, [name].,  
57 and colleagues will present their data indicating a contemporary arthrofibrosis rate of 5.8 percent  
58 after primary TKA at Mayo Clinic. In addition, 2.8 percent of patients require a manipulation  
59 under anesthesia (MUA). While there are alternatives to MUA, physical therapy shows only  
60 modest gains and surgery is reserved for patients that fail non-operative management. With  
61 MUA, mean flexion improved 35 degrees. However, 5 percent of patients failed to maintain at  
62 least 90 degrees of flexion after the MUA at our institution. More concerning, these results were  
63 similar to the previous decade, where the rate of arthrofibrosis was 5.4 percent, with 2.9 percent  
64 requiring MUA. The only identifiable risk factor for MUA was previous knee operation. Lastly,  
65 a manipulation under anesthesia significantly increased the risk for revision. As one can see, the  
66 incidence of arthrofibrosis following primary TKA has remained unchanged over the past two  
67 decades. With the exponential increase in primary TKAs, arthrofibrosis is a large burden to the  
68 patient, surgeon and entire U.S. health care system (\$8.75 billion annually).

69

70 Preliminary clinical and translational research has indicated that an inflammatory disorder of the  
71 musculoskeletal system may be responsible for post-operative stiffness in some patients.  
72 Although evidence remains limited to animal models, the inflammatory cascade plays a central  
73 role in the formation, and recurrence, of arthrofibrosis, particularly at the time of insult (i.e. time  
74 of index arthroplasty and/or MUA). This is essential as some insurance companies have  
75 stopped covering this procedure. The purpose of this study was to determine the efficacy of  
76 manipulation under anesthesia (MUA), with and without perioperative oral celecoxib and  
77 intravenous (IV) corticosteroid.

78

## 79 **PATIENTS AND METHODS**

### 80 ***Study Design***

81 This study is a prospective, multicenter, randomized clinical trial (RCT) designed to evaluate the  
82 use of anti-inflammatory medications for the management of arthrofibrosis following primary  
83 TKA. Patients will be randomly assigned to either the control or experimental group. Both groups  
84 will receive a manipulation under anesthesia (MUA) if flexion is < 90 degrees at 4 –12 weeks  
85 postoperatively. Manipulation under anesthesia is the international standard of care for early  
86 arthrofibrosis. The control group will not receive any IV corticosteroids or PO non-steroidal anti-  
87 inflammatory medications (NSAIDs). The experimental group will receive a single dose of IV  
88 corticosteroids (8 mg IV dexamethasone immediately prior to MUA) and 2 weeks of PO celecoxib  
89 at a dose of 200 mg daily. Many surgeons, including several at the Mayo Clinic, consider the use  
90 of IV corticosteroids and PO celecoxib the standard of care with a MUA.

91

92 ***Patients***

93 Patients will be recruited from sixteen high-volume, academic, tertiary-care referral centers  
94 (Table 1). All enrolling centers have been vetted, as only surgeons that are members of the  
95 prestigious closed Knee Society (representing the top 100 knee surgeons in the world) are  
96 participating. Patients approached for enrollment will have received a primary unilateral TKA  
97 for a diagnosis of osteoarthritis. All primary TKA constructs will have constraint that is less than  
98 that of varus-valgus constraint (VVC). All VVC and hinged TKAs will be excluded. Only  
99 MUAs scheduled between 4 –12weeks postoperatively will be included.

100

101 Institutional Review Board (IRB) approval will be obtained from all respective institutions prior  
102 to initiation of the study. The Mayo Clinic will serve as the coordinating site. Patients will be  
103 excluded from the study if any of the following exist: (1) intolerance to NSAIDs, (2) renal  
104 dysfunction, (3) age < 18 or > 90 years, (4) primary diagnosis of rheumatoid arthritis and (5)  
105 patients with GFR <60 as the cut off for CKD (stage 3 CKD). Use of non-steroidal anti-  
106 inflammatory medications during the first two weeks after manipulation under anesthesia will  
107 exclude patients from participation in this study. However, celecoxib (a non-steroidal anti-  
108 inflammatory medication) will be provided for those patients randomized to the experimental  
109 group, once daily for fourteen days following the manipulation under anesthesia. Aspirin, used  
110 routinely for DVT prophylaxis post-operatively, did not restrict patients from participation in this  
111 study. Patients who are on NSAIDs prior to MUA, is ok to enroll. Patient demographics were  
112 noted, including age at index arthroplasty, sex, body mass index (BMI), ASA score, and  
113 Charlson Index.

114

115 ***Randomization***

116 Patients will be randomized into one of 2 groups: (1) MUA only (i.e. control group) or (2) MUA  
117 plus 8 mg of IV dexamethasone immediately before MUA, followed by 2 weeks of PO celecoxib  
118 (200 mg daily) (experimental group). Assignment of patients into either group will be made prior  
119 to the initiation of enrollment for the study. Patients will be randomized using a computer  
120 generated (SAS PROC) block randomization schedule to ensure equivalent numbers of patients  
121 in each group over the course of the study in case early stopping is required. The randomization  
122 schedule will be generated by the Mayo Clinic Department of Epidemiology and Biostatistics  
123 with the randomization list provided to the investigators prior to initiation of patient recruitment.  
124 Neither the patient nor the treating physician were blinded the randomization group.

125

126 ***Manipulation Under Anesthesia***

127 Patients will undergo MUA per their institutional protocol. As previously noted, these will be  
128 completed between 4 and 10 weeks postoperatively for flexion < 90 degrees. Patients will  
129 receive sedation per their institutional protocol. Physical therapy (either supervised or  
130 unsupervised) will be prescribed 2 -3 times per week for 4 – 6 weeks thereafter.

131

132 ***Outcome Measures***

133 The primary outcome measure will be knee range of motion, including both passive and active  
134 flexion and extension 6 weeks after the manipulation and 1 year from the date of the TKA.  
135 Secondary outcomes will include comparison of Knee Society Scores (KSS), 12-item Short  
136 Form Survey (SF-12v2), Knee Injury and Osteoarthritis Outcome Score (KOOS), and the  
137 Promise-29 outcome form (Appendices 1-4). Outcomes will be documented pre-MUA, 6 weeks

138 after the MUA, and 1 year after the TKA. A standardize evaluation form will be shared amongst  
139 all participating sites, and will be used consistently for all patients (Appendix 1-4).

140

141 ***Power Analysis***

142 The mean and standard deviation for sample size calculation were derived from a study by  
143 Yercan et al. In that study, the authors found that the mean ROM following MUA was  $114^\circ \pm$   
144  $16^\circ$ . We hypothesized that a  $10^\circ$  difference in total range of motion would constitute a  
145 clinically significant difference. With a type I error rate of 5%, 108 total patients (54 per arm) are  
146 required to have 90% power to detect this difference. Accounting for a dropout rate of 20%, 65  
147 patients per arm (130 total patients) will be recruited.

148

149 ***Statistical Analysis***

150 All data will be summarized and reported descriptively using appropriate summary statistics,  
151 including mean and standard deviation (SD) for continuous variables, and count and percentage  
152 for categorical variables. The analysis was focused on the two primary study outcomes: range of  
153 motion (total arc of motion as well as angle of terminal knee flexion, measured in degrees), and  
154 subjective outcome (KSS, SF-12v2, KOOS, and PROMIS). Outcomes were compared between  
155 the two study groups using two-sample t-tests if the data are approximately normally distributed;  
156 if the data are not sufficiently normally distributed, non-parametric Wilcoxon rank sum tests was  
157 used. Since the subjects were assigned to the study groups in a randomized manner, no  
158 significant differences between the subjects in the two groups were expected. However,  
159 apparent differences in subject demographics or baseline clinical data were evaluated, and  
160 further analysis was undertaken using multivariable modeling to compare the two groups while

161 adjusting for other important variables. When necessary and appropriate, the analysis was  
162 adjusted for enrolling center. Categorical outcomes were analyzed using chi-square tests and  
163 logistic regression. Separate analyses were performed for the 6-week and 1-year outcomes. All  
164 statistical tests were two-sided and p-values less than 0.05 will be considered significant.

165

166 ***Sources of Funding***

167 This study is partially supported by the Knee Society Branded Multi-Center Randomized Clinical  
168 Trial Grant.

169  
170  
171  
172  
173  
174  
175  
176  
177  
178  
179  
180  
181  
182  
183  
184  
185  
186  
187  
188  
189  
190  
191  
192  
193  
194  
195  
196  
197  
198

199  
200  
201  
202  
203  
204  
205  
206  
207  
208  
209  
210

211 **TABLES**

212  
213

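### Excluding patients for NSAID use in the two weeks after MUA would, if followed as written, select after randomisation, and no stated analysis set keeps those patients

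*Combined protocol and SAP*

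**What the plan says.** All references are to the combined protocol and SAP, under Patients and Methods.

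- **Patients.** After five numbered exclusions comes an unnumbered sentence on use of non-steroidal anti-"inflammatory medications during the first two weeks after manipulation under anesthesia will" "exclude patients from participation in this study. However, celecoxib (a non-steroidal anti"-"inflammatory medication) will be provided for those patients randomized to the experimental" group. The exception covers celecoxib for the fourteen days after MUA.
- **Patients, next two sentences.** Aspirin, used "routinely for DVT prophylaxis post-operatively, did not restrict patients from participation in this" study. On earlier use: "Patients who are on NSAIDs prior to MUA, is ok to enroll".
- **Study Design.** "The control group will not receive any IV corticosteroids or PO non-steroidal anti"-inflammatory drugs.
- **Randomization.** The experimental arm has MUA "plus 8 mg of IV dexamethasone immediately before MUA, followed by 2 weeks of PO celecoxib". The allocation schedule is produced before recruitment starts. On blinding: "Neither the patient nor the treating physician were blinded the randomization group".
- **Statistical Analysis.** The two study groups are compared by t-test or Wilcoxon test, separately at 6 weeks and 1 year. No intention-to-treat, as-randomised or per-protocol set is named. There is no rule for a patient who takes a non-study NSAID and no missing-data method.
- **Power Analysis.** The only allowance for loss is a 20% dropout rate.

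**The concern.** The trigger is use of a drug in a window that opens at MUA. The experimental arm's first study drug is given just before MUA, so allocation must already be in effect when the window opens. Actual use can be seen only in patients who have been randomised.

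Three features make the trigger potentially unequal between arms. Only the experimental arm is supplied an NSAID, patients already taking NSAIDs may enrol, and patients and treating physicians know the allocation. A control patient with a painful or stiff knee might be more likely to take an NSAID than a patient already on celecoxib. The documents give no rates, so this is plausible but not shown.

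Statistical Analysis relies on random assignment to make the groups comparable. That holds for the patients randomised. It need not hold for those left after some are removed for what they did later. With sixteen centres, an ambiguous rule may also be applied differently from site to site.

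**Working it through.** **1. The plan's own figure.** Inputs from Power Analysis and Statistical Analysis: SD 16, difference 10, two-sided 5%, 90% power. Per arm, n = 2 × (1.960 + 1.282)² × 16² / 10² = 53.8, so 54, or 108 in total. This reproduces the plan. Recruiting 65 per arm and losing 20% leaves 65 × 0.8 = 52 per arm. Two-sided t-test power at 52 per arm is 88%.

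**2. Order of events.** Schedule produced, patient allocated, dexamethasone (experimental arm), MUA, two-week window, outcomes at 6 weeks and 1 year. The trigger falls after allocation and before every post-MUA outcome.

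**3. Three readings of the sentence.**

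| Reading | Selects after randomisation? | What is left open |
|---|---|---|
| Planned use, judged before enrolment | No | Analysis set unstated |
| Restriction on other medication, patient stays in the study | No, if follow-up continues and data are used | Analysis set unstated |
| Actual use ends participation | Yes, if the patient is dropped | Bias possible |

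The documents do not choose between them.

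**4. Form of the bias under the third reading.** Let p be the share excluded in an arm and gap the mean range of motion of retained minus excluded patients. The full-arm mean is (1 − p) × retained + p × excluded, so the retained mean exceeds it by p × gap. The estimated benefit (experimental minus control) is therefore understated by

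bias = p(control) × gap(control) − p(experimental) × gap(experimental),

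and overstated if this is negative. It is zero only if the two products are equal. Equal exclusion rates alone do not ensure that.

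**5. Illustration.** The documents give no rates or gaps, so all of these are assumed: a gap of 8 degrees (half an SD) in either direction, exclusions in the control arm only, on top of the 20% dropout. For 10%, bias = 0.10 × 8 = 0.8 degrees. With 52 and 47 patients, SE = 16 × √(1/52 + 1/47) = 3.22.

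| Controls excluded | Patients (exp./control) | Bias, degrees | Power if excluded would have done worse | Type I error if excluded would have done better |
|---|---|---|---|---|
| 5% | 52/49 | 0.4 | 85% | 5.2% |
| 10% | 52/47 | 0.8 | 81% | 5.7% |
| 20% | 52/42 | 1.6 | 71% | 7.6% |

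The 20% row means 1 − 42/65 = 35% of controls lost in all. Part of the power loss is smaller numbers: 52/42 with no bias gives 85%.

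**6. Cost of keeping everyone.** Suppose 10% of controls use NSAIDs and gain half to all of the 10-degree benefit. The difference falls by 0.10 × 5 = 0.5 or 0.10 × 10 = 1.0, to 9.5 or 9.0 degrees. Power at 52 per arm is then 85% or 81%.

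**The case against.** The best case for the plan is that the paragraph is about enrolment. The sentence follows the baseline exclusions, uses the same language of exclusion, and precedes two notes on who may take part. The Study Design statement that controls receive no oral NSAIDs also fits a restriction on other medication. No section says that a randomised patient is withdrawn, that follow-up stops or that data are deleted. The reliance on random assignment is compatible with analysing patients as randomised. Every number for the bias is assumed, and at 5% exclusion the effect on type I error is negligible.

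Much of this stands. A reader might infer that the plan intends to remove NSAID users from the analysis, or that the result will be biased in favour of the experimental arm. The documents support neither: removal of data is not stated, and the direction depends on who takes NSAIDs, which is not given.

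The ambiguity remains. The sentence refers to use, not intended use, in a period that cannot be observed at enrolment, and it stands outside the numbered list. A site that follows it as written would exclude randomised patients, and nothing in Statistical Analysis would keep them in. The promise to summarise all data concerns descriptive reporting and does not say who is analysed or in which arm.

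**Conclusion.** The point holds as a risk created by the wording together with the missing analysis set. It should be fixed, but it is not evidence of a planned exclusion from analysis. If the sentence is only a screening criterion, no selection follows and just the analysis-set statement is missing.

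If the rule is applied after MUA and those patients are dropped, the bias is the difference of the two products in step 4, and the documents do not determine its size or sign. On the assumed 8-degree gap with control-only exclusions of 5% to 20%, it runs from 0.4 to 1.6 degrees against a target of 10, with type I error between 5.2% and 7.6% in the unfavourable direction. These values show scale and are not estimates.

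A reader might also infer that keeping all patients would raise power. It need not: at 10%, dilution costs about as much power as exclusion does. The gain is a preserved randomised comparison.

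**What to change.** 1. State whether the sentence is a criterion judged before randomisation or a restriction after MUA, and reconcile it with the neighbouring enrolment notes.
2. For follow-up and analysis only, state that non-study NSAID use after MUA does not remove a randomised patient. Record such use by arm and keep collecting the 6-week and 1-year outcomes.
3. Add one line to Statistical Analysis: the primary analysis includes all randomised patients with outcome data, in the arm assigned. Any analysis leaving out NSAID users is a sensitivity analysis.

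This costs one clarified sentence, one added line, a record of NSAID use in both arms, and follow-up at visits already planned. The downside is the dilution in step 6: power falls from 88% to about 85% to 81% on those assumptions. The change does not affect what patients may take or whether study treatment continues. It also leaves untouched any bias from ordinary dropout, for which the plan allows 20% and gives no missing-data method.

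### The randomisation list goes to the investigators before recruitment in an unblinded trial, so allocation is not concealed and enrolment can be steered.

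*Combined protocol and SAP*

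**What the plan says.** All of the allocation procedure is in Patients and Methods, Randomization:

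- Timing: "Assignment of patients into either group will be made prior" to the start of enrolment.
- Method: a computer-"generated (SAS PROC) block randomization schedule to ensure equivalent numbers of patients" in each group. Block size, varying blocks and stratification by site are not stated.
- Custody: the coordinating site's epidemiology and biostatistics department produces the schedule, "with the randomization list provided to the investigators prior to initiation of patient recruitment".
- Blinding: "Neither the patient nor the treating physician were blinded the randomization group".

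Study Design adds a statement about treatment preference: "Many surgeons, including several at the Mayo Clinic, consider the use" "of IV corticosteroids and PO celecoxib the standard of care with a MUA".

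No section describes a concealment step. There is no web or telephone allocation, no sealed envelopes, no independent holder of the list, and no requirement that consent, eligibility and baseline measurement be complete before the assignment is revealed.

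**The concern.** Allocation concealment means that whoever decides on entry cannot know the next arm. It is separate from blinding, which applies after assignment, and an open-label trial can conceal allocation fully. This plan gives up concealment by its own rule.

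- **Opportunity.** A list holder can foresee the arm before approaching a patient, confirming that flexion is below 90 degrees, scheduling the MUA, or recording baseline range of motion.
- **Motive.** The plan itself reports that many surgeons already regard the experimental regimen as standard.
- **No backstop.** Patients and treating physicians are unblinded. Statistical Analysis relies on random assignment to expect comparable groups. If recruiters can foresee the arm, that expectation is no longer secured by the design.

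The risk is selection bias in the between-arm comparison. A larger sample does not reduce such a bias; it only makes a biased estimate look more precise.

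**Working it through.** **1. Reproduce the plan's own figure.** Inputs from Power Analysis and Statistical Analysis: difference 10 degrees, SD 16 degrees, two-sided α = 0.05, power 90%.

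n per arm = 2 × (1.960 + 1.282)² × 16² / 10² = 53.8, rounded up to 54, or 108 in total. This matches the plan. Concealing the list does not change it.

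**2. Evaluable patients.** The plan recruits 65 per arm and allows 20% dropout: 65 × 0.80 = 52 per arm.

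**3. Standard error of the difference.** 16 × √(2/52) = 3.14 degrees.

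**4. Illustrative bias.** Suppose a net fraction *f* of one arm is replaced by patients whose expected outcome differs by a gap *g*. The mean difference shifts by b = f × g. Neither *f* nor *g* is in the documents; both are assumptions.

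**5. Type I error with no true effect.** With k = b / 3.14, the two-sided rejection probability (normal test) is Φ(−1.96 + k) + Φ(−1.96 − k).

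| f | Bias, g = 16 (1 SD) | Type I error | Bias, g = 8 (0.5 SD) | Type I error |
|---|---|---|---|---|
| 10% | 1.6° | 8.0% | 0.8° | 5.7% |
| 20% | 3.2° | 17.5% | 1.6° | 8.0% |
| 30% | 4.8° | 33.4% | 2.4° | 11.9% |

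Worked line for 3.2 degrees: k = 3.2/3.14 = 1.02; Φ(−0.94) + Φ(−2.98) = 0.1736 + 0.0014 = 0.175.

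**6. Cross-check.** The noncentral t distribution at the plan's 54 per arm gives 6.2%, 9.9%, 16.2%, 25.1% and 36.3% for biases of 1, 2, 3, 4 and 5 degrees. The scale is the same.

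**7. How much the open list adds to blocking.** Take an assumed fixed block size of 4, known to recruiters in an unblinded trial, with the list hidden. Enumerating all blocks, 33% of assignments are certain in advance and the best guess is right 71% of the time. For a holder who knows the current position, an open list makes 100% certain.

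**The case against.** The strongest reply is that this reads the sentence at its worst.

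- **Who holds the list.** The word investigators might mean only the coordinating team. The text does not say so, and Mayo Clinic, the coordinating site, is itself an enrolling centre (Table 1). Exposure would be much smaller, though: if recruitment were equal across sixteen sites (an assumption), 20% steering at one site is 1.25% overall, or 0.0125 × 16 = 0.2 degrees with a 1 SD gap. The sentence would still need correcting.
- **Position on the list.** The plan does not say whether there is one shared list or one per site. With a shared list, a recruiter would also need to know how many patients the other sites had enrolled. That would hide the next arm only in part, and it is not offered as a safeguard.
- **Size.** The steered fraction and the prognostic gap are not documented. The 16 degrees is the spread of post-MUA motion in a cited study, not a difference a surgeon is known to foresee among patients who all have flexion below 90 degrees. This stands: the figures are scenarios and do not carry the conclusion.
- **Direction.** Surgeons who favour the regimen might direct their stiffest knees to it, which would bias against it. This also stands. The error rates above are two-sided and do not depend on direction, but no bias in favour of the experimental arm has been shown.
- **Adjustment.** The plan will examine baseline differences, adjust by multivariable modelling, and account for centre where needed. That helps with measured variables, including baseline motion. It cannot reach selection on unrecorded prognosis, such as expected adherence to physical therapy.

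Fixing the schedule before enrolment is ordinary practice and no fault in itself. The fault is releasing it.

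**Conclusion.** The concern holds and must be fixed. The plan states a rule that, if followed, removes allocation concealment in an unblinded trial, and nothing elsewhere restores it. This is a wrong rule rather than a missing detail.

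The conclusion rests on the text and not on the size of any steering, which is unknown and need not have happened. As an illustration, a bias of 3.2 degrees is about a third of the 10-degree target difference and would raise the false-positive rate to 3.5 times its nominal level (17.5% against 5%). That scenario assumes 20% net steering in one arm, a 1 SD gap, and 52 evaluable patients per arm. With weaker steering, or a list confined to one site, the effect could be small.

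**What to change.** Replace the sentence on custody of the list with wording such as:

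> The randomisation schedule will be held by the Department of Epidemiology and Biostatistics and will not be available to any enrolling investigator or site staff. Each assignment will be released, by a web or telephone system or by sequentially numbered opaque sealed envelopes, only after consent, eligibility and pre-MUA range of motion have been recorded. Block sizes will vary at random and will not be disclosed to sites.

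State also whether there is one schedule or one per site. The varying blocks are secondary; withholding the list is the essential change.

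If patients have already been enrolled (the text mixes tenses), document who held the list and when, and report this as a limitation.

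The cost is protocol wording plus a standard central release module or a set of envelopes. The department that would hold the list already generates it. Sample size, visits, treatment and assessors are unchanged.

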**Table 1. List of participating institutions included**

Aria 3B Orthopaedic Specialists  
Colorado Joint Replacement  
Duke University Medical Center  
HipKnee Arkansas Foundation  
Hospital for Joint Diseases  
Hospital for Special Surgery  
Houston Methodist  
Joint Implant Surgeons  
Mayo Clinic  
New York-Presbyterian at Columbia University  
OrthoCarolina  
Rothman Institute  
Rush University Medical Center  
  
Cleveland Clinic  
University of Nebraska Medical Center  
University of Utah Orthopaedic Center

214  
215  
216  
217  
218  
219  
220  
221  
222  
223  
224  
225  
226

227  
228  
229  
230  
231  
232  
233  
234  
235  
236  
237  
238

239 **Table 2.** Baseline demographics and clinical characteristics

Demographic and Clinical Characteristics	MUA (N = X)	MUA + AI (N = X)
Demographic Characteristics		
Age (year)		
Sex (female/male) (no. of patients)		
Weight (kg)		
Height (cm)		
BMI (kg/m  )		
ASA Status (no. of patients)		
Implant Type		
Range of Motion		
Total		
Flexion Contracture		
Extension Deficit		

240  
241  
242  
243  
244  
245  
246  
247  
248  
249  
250  
251

252

253

254

255

256

257 **Table 3.** Outcome following manipulation under anesthesia for stiffness after total knee  
 258 arthroplasty

Blood Loss, Drain Output, and Rate of Blood Transfusions	MUA (N = X)	MUA + AI (N = X)	p value
Six Week ROM Total Pre-Manipulation Flexion Total 6 weeks Post-MUA Flexion < 90 degrees < 80 degrees Total 6 weeks Post-MUA Flexion < 90 degrees < 80 degrees			
Six Week Subjective Outcome KSS SF-12v2 KOOS Promis 29			

Blood Loss, Drain Output, and Rate of Blood Transfusions	MUA (N = X)	MUA + AI (N = X)	p value
One Year ROM Total Pre-Manipulation Flexion Total 6 weeks Post-MUA Flexion < 90 degrees < 80 degrees Total 6 weeks Post-MUA Flexion < 90 degrees < 80 degrees			
One Year Subjective Outcome KSS SF-12v2 KOOS Promis 29			

259

260

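### The operator can know the arm while manipulating the knee, and no end-of-manipulation ROM is scheduled, so a difference in manipulation between arms could not be told apart from a drug effect

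*Combined protocol and SAP*

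**What the plan says.** Four parts of the combined protocol and SAP bear on this.

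- **Knowledge of the arm.** Randomization states: "Neither the patient nor the treating physician were blinded the randomization group". The schedule is generated centrally, "with the randomization list provided to the investigators prior to initiation of patient recruitment". The experimental arm is MUA "plus 8 mg of IV dexamethasone immediately before MUA, followed by 2 weeks of PO celecoxib". No placebo is described for controls.
- **The manipulation.** Under Manipulation Under Anesthesia: "Patients will undergo MUA per their institutional protocol". No target motion or end-point common to the sites is given.
- **Prior belief.** Study Design says "Many surgeons, including several at the Mayo Clinic, consider the use" of the two drugs to be standard of care with an MUA.
- **What is measured.** Under Outcome Measures: "Outcomes will be documented pre-MUA, 6 weeks" "after the MUA, and 1 year after the TKA". The Table 3 shell has pre-manipulation rows and rows labeled "Total 6 weeks Post-MUA Flexion", and none for the end of the manipulation.

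The primary outcome is ROM at 6 weeks after the MUA and 1 year after the TKA. Statistical Analysis compares the arms at each time, with possible adjustment for baseline variables and for enrolling center.

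**The concern.** ROM at 6 weeks is the motion reached at the table less the motion lost afterwards. The Introduction argues that inflammation drives the formation and recurrence of arthrofibrosis, so the drug hypothesis is mainly about the second component. The first is in the hands of the operator, who can know the arm and may have a view on the drugs.

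If knowing the arm changed how far the knee was taken, the difference would pass into 6-week and 1-year ROM. Nothing in the planned analysis would remove it, because it would arise after baseline and within center. Masking the examiner at 6 weeks would not help either: that examiner would be measuring a knee that had already been manipulated differently. This is therefore a separate question from who takes the follow-up readings.

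**Working it through.** **Inputs.** From Power Analysis: SD 16 degrees, target difference 10 degrees, type I error 5%, power 90%, 54 per arm. From Statistical Analysis: two-sided tests. The shifts and retention fractions below are assumptions; the documents give none.

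**1. Reproduce the plan's figure.** n per arm = 2 × [16 × (1.960 + 1.282) / 10]² = 53.8, rounded up to 54. This agrees with the plan.

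**2. Precision of the comparison.** SE = 16 × √(2/54) = 3.08 degrees. An observed difference of about 1.96 × 3.08 = 6.0 degrees is significant.

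**3. No drug effect, shift of d degrees at 6 weeks due to the manipulation alone.** The probability of a significant result is 1 − Φ(1.96 − d/3.08) + Φ(−1.96 − d/3.08):

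| Shift at 6 weeks (degrees) | Probability of significance |
|---|---|
| 0 | 5% |
| 2 | 10% |
| 3 | 16% |
| 5 | 37% |
| 8 | 74% |

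**4. Partial retention.** If half of the extra table gain is lost by 6 weeks, 3 and 5 degrees at the table become 1.5 and 2.5 degrees, and the same formula gives about 8% and 13%.

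**5. The opposite direction.** Suppose the drugs truly add 10 degrees and operators gain 3 or 5 degrees more in controls, fully retained. The net difference is 7 or 5 degrees, and power falls from 90% to Φ(7/3.08 − 1.96) ≈ 62% or Φ(5/3.08 − 1.96) ≈ 37%.

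**6. What an end-of-manipulation reading could show.** With 54 per arm, the 95% CI half-width is 1.96 × SD × √(2/54). The documents give no SD for this reading, so 8 to 16 degrees is an assumed range. Power is from the noncentral t.

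| Assumed SD (degrees) | CI half-width (degrees) | Power to detect a 5-degree imbalance |
|---|---|---|
| 8 | 3.0 | 90% |
| 10 | 3.8 | 73% |
| 12 | 4.5 | 57% |
| 16 | 6.0 | 36% |

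The reading is a useful check, but it could easily miss a 5-degree imbalance if the SD is near the upper end of that range.

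**Scale.** The Introduction reports a mean flexion improvement of 35 degrees with MUA. A 5-degree shift is 5/35 = 14% of that.

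**The case against.** The strongest reply is that the mechanism is conjecture. Believing in a drug is not the same as manipulating differently, and no passage says that technique varies by arm. This stands. A reader might infer that operators push harder in the experimental arm and that the trial is biased toward the drugs. The documents support neither step. An operator who trusts the drugs might equally do more for a control knee that will not receive them.

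Further points, and what remains of them:

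- **Institutional technique produces variation between sites, not between arms.** Correct. Both arms at a site share its protocol, and center adjustment is allowed for. The lack of a common end-point matters only because it leaves room for discretion within a site.
- **The larger error rates assume that the whole table gain persists.** Correct, which is why the half-retention figures are given beside them.
- **A reading at the end of the MUA would not settle the matter.** Correct. A reader might infer that it would expose any imbalance or prove equal manipulation; step 6 shows otherwise. It could also be biased if an unmasked operator takes it.
- **The absence cannot be fully verified.** Partly right. Appendices 1–4, which include the standardized form, are not in the text reviewed, and the Table 3 shell is visibly unfinished: its header concerns blood loss and its 6-week rows are repeated. The claim is therefore limited to the stated schedule and table shell. That the treating physician is the operator is also an inference, though a strong one given the drug timing and the list.
- **Open-label delivery is disclosed, and the stated aim is to compare MUA with and without the drugs.** True. But a difference in manipulation caused by knowing the arm would still make it hard to attribute the result to the drugs.

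**Conclusion.** The point holds in conditional form. The plan lets the operator know the arm during the manipulation, and its stated schedule has no ROM reading at the end of it. If the manipulation differed by arm, 6-week and 1-year ROM could not separate that from a drug effect, and the bias could run either way.

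With the plan's own SD and sample size, an assumed 3- to 5-degree shift at 6 weeks raises the chance of a false positive from 5% to between 16% and 37%. A 3- to 5-degree table gain that is half retained gives 8% to 13%. The reverse shift, fully retained, cuts power for a true 10-degree effect to between 62% and 37%. These figures illustrate sensitivity and do not estimate an actual bias. The issue is worth correcting because the remedy is cheap and the exposed endpoint is the primary one.

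**What to change.** 1. **Mask the operator until the manipulation is complete.** Amend the Randomization sentence that gives investigators the list. The schedule can still be generated in advance, but the assignment should be held by the coordinating center or the site's anesthesia team and released to the operator only once the manipulation and its reading are done. Without this change of custody, asking anesthesia to keep the assignment quiet achieves nothing. Amend the blinding sentence to match. The allocated regimen is unchanged. Only the IV dose precedes the MUA, so only that dose has to be kept from the operator's view.
2. **Record passive flexion and extension at the end of the manipulation**, before the arm is revealed, on the standardized form. Report both by arm in Table 3 with a confidence interval, as a descriptive check. Do not present the result as proof of equal manipulation, and do not use it as a covariate in the primary analysis, since it is measured after randomization. If change from the end of the MUA to 6 weeks is reported, use passive ROM at both times and label it supportive.

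**Cost.** One reading during a procedure already under way and one field on an existing form, with no extra visit, staff or patients. The real burden is moving list custody and coordinating release at sixteen centers. Some operators may still learn the arm; recording when that happens would be sensible.
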